### Analysis Population

The safety population consists of all patients who are implanted with the study device. The primary analysis for all safety endpoints will be performed on this population.

The analysis for all primary and secondary study endpoints and baseline, procedural and follow-up characteristics will be performed on an intent-to-treat analysis population which will include all available data for all enrolled subjects. Standard summary statistics will be calculated for all study variables.

 Cerus Endovascular	Document Number DNQS428-01	Rev. F	Page 46 of 119
Clinical Investigation Plan	Title		
Confidential & Proprietary	Coil Assisted Flow Diversion: A prospective, single arm, multi-center study to assess the safety and performance of Neqstent in adjunctive therapy (CAFI Study)		

The primary safety endpoint will be calculated as the proportion of subjects with death of any nonaccidental cause or any major stroke within the first 30 days after treatment or major stroke or death due to neurological cause from day 31 to 6 months after treatment.

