
 
Cerus Endovascular
	
Document Number DNQS428-01
	
Rev. F
	
Page 33 of 119

Clinical Investigation Plan
	
Title
		

Confidential & Proprietary
	
Coil Assisted Flow Diversion: A prospective, single arm, multi-center study to assess the safety and performance of Neqstent in adjunctive therapy (CAFI Study)
		

All patients must sign a study-specific consent form prior to the commencement of any protocol-specific assessments and/or procedures. Final qualification will occur during the implant procedure due to the need for confirmation of IA appropriateness with cerebral angiography.

The patient is enrolled at the time of consent and is considered a study subject in the reporting analysis group only when the patient is fully qualified and at least one Neqstent device has been placed into the patient's body. The following listing provides examples of patient enrollment scenarios for the study:

- The patient is not considered enrolled but not included in the primary analysis group in the study: if at the onset of the procedure in the initial DSA, the investigator determined the patient's IA was not suitable for treatment with the device, thus, no attempt was made by the investigator to place the device. The patient will be treated outside of the study per the investigator's usual practices. The reason for not treating the patient must be documented on a study exit form. The patient is not included in the primary analysis group because the Neqstent was never opened or deployed inside the patient. All patients will be listed in the final report.
- The patient is considered enrolled but not included in the primary analysis group in the study: at the onset of the procedure, the investigator determined the subject's IA was suitable for treatment with the device. The investigator attempted but was unable to place the device within the IA and the subject required alternative treatment. The subject is considered enrolled for the purposes of the study but will only be followed through the 1-month visit. All failed implant attempts will be reported in the final report.

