## 10.2 Patient Population

Two patient populations will be considered in the analyses, an Intent-to-Treat (ITT) population and a Per Protocol population (PP). The ITT population includes all patients. The PP population will include subjects who complete 6 months of follow-up, die prior to their 6-month clinic visit, or are study failure (withdrawal from study to obtain alternate treatment). The PP will exclude patients with any major protocol violation that affects proper study inclusion or significant outcomes. Endpoints will be evaluated in the PP and ITT populations.

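### The analysis labelled primary for safety covers implanted patients only, so a death or major disabling stroke in a failed Neqstent attempt falls outside the primary rate; the ITT analysis of the same endpoint has no stated role

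*Combined protocol and SAP*

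**What the plan says.** Section 10.6, Analysis Population, holds two rules for the primary safety endpoint. The first paragraph reads "The safety population consists of all patients who are implanted with the study device", followed by "The primary analysis for all safety endpoints will be performed on this population". The second paragraph says that the analysis of all primary and secondary endpoints "will be performed on an intent-to-treat analysis population which will include all available data for all enrolled subjects".

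Section 10.2 names only an ITT and a per-protocol population. It says "The ITT population includes all patients" and "Endpoints will be evaluated in the PP and ITT populations", and does not mention a safety population.

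Section 7.5 (repeated in the Synopsis under Enrollment and Eligibility) sorts patients by what happened in the procedure. For the case "The investigator attempted but was unable to place the device within the IA and the subject required alternative treatment", the status is "The patient is considered enrolled but not included in the primary analysis group in the study". The same section says "The patient is enrolled at the time of consent", yet describes a patient found unsuitable on the initial angiogram, with no attempt made, as not considered enrolled.

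The endpoint (Section 10.4.1) counts non-accidental deaths and major disabling strokes in the first 30 days after treatment, then neurological deaths and major disabling strokes up to 6 months.

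**The concern.** Membership of the set labelled primary depends on the outcome of the procedure. The first 30 days of the endpoint include procedural harm, and a serious complication during delivery can itself be the reason that the device is not placed. Section 7.7.4 makes detachment the last step, after the sac has been coiled, so there is a period of exposure before a patient becomes an implanted patient. A set chosen on successful placement describes the risk of completed implants. A physician or notified body deciding about the device also needs the risk of setting out to use it.

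The second issue is the missing sentence on the role of ITT. Two paragraphs in one section analyse the same endpoint in different sets, and a report could show two safety proportions without the plan having said how they relate.

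**Working it through.** **1. The plan's own figure.** The plan gives no expected safety rate. Its sample size of 46 evaluable (Section 10.6) reproduces from 70%, 55%, a 10% margin, one-sided 5% and 80% power: (0.55 × 0.45 + 0.70 × 0.30) × (1.645 + 0.842)² / 0.25² = 45.3, rounded up to 46; 46 × 1.1 = 50.6, rounded up to 51. The point does not depend on this; 51 is used below only as the number implanted, as in the Synopsis under Study Size and Duration.

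**2. Who is in which set.**

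| Patient | Safety set (10.6) | Primary analysis group (7.5) | ITT (10.6) | ITT (10.2) |
|---|---|---|---|---|
| Consented, no attempt | out | out | unclear: enrolled at consent, then not considered enrolled | in |
| Attempted, not placed | out | out | in | in |
| Placed | in | in | in | in |

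No column isolates the patients exposed to an attempt. The first two omit failed attempts; the last two include them but may add unexposed patients.

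**3. Assumed inputs.** The documents give no Neqstent placement rate. Section 4 quotes 93% for another intrasaccular device; 51/0.93 = 54.8, so about 55 attempts and 4 failures. An assumed 98% gives 51/0.98 = 52.0, so 52 attempts and 1 failure. Event counts are also assumed.

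**4. Effect on the safety rate.** With x events among 51 implanted and y among k failed attempts, the implanted rate is x/51 and the attempted rate is (x + y)/(51 + k). Intervals are exact 95%.

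| x | y | k | Implanted | Attempted |
|---|---|---|---|---|
| 1 | 1 | 4 | 1/51 = 2.0% (0.05 to 10.4%) | 2/55 = 3.6% (0.4 to 12.5%) |
| 1 | 1 | 1 | 1/51 = 2.0% | 2/52 = 3.8% (0.5 to 13.2%) |
| 0 | 1 | 4 | 0/51 = 0% (0 to 7.0%) | 1/55 = 1.8% (0.0 to 9.7%) |
| 1 | 0 | 4 | 1/51 = 2.0% | 1/55 = 1.8% |
| 1 | 0 | 1 | 1/51 = 2.0% | 1/52 = 1.9% |

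**5. Direction.** With one implanted event and an event rate r in failed attempts, the expected attempted rate is (1 + k·r)/(51 + k). For k = 4 this is 1.8% at r = 0, 1.2/55 = 2.2% at r = 5% and 1.4/55 = 2.5% at r = 10%. The two rates are equal at r = 1/51 = 1.96%. Above that the implanted rate is too low, below it too high.

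**6. How often it would matter.** The chance of at least one failed placement in 51 attempts is 1 − 0.98^51 = 64% at a 2% failure rate and 1 − 0.93^51 = 98% at 7%. The chance of at least one event among 4 failed attempts at r = 5% is 1 − 0.95⁴ = 19%. So a failed attempt is likely, but an event in one is not.

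**7. ITT as a substitute.** If 5 consented patients with no attempt (assumed) also entered ITT, 2/55 would become 2/60 = 3.3%.

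**8. Follow-up of failed attempts.** Section 7.5 follows them only to the 1-month visit. Table 8 allows one week either side, so an early visit could fall at about day 30 − 7 = 23. The Synopsis (Study Size and Duration) and Section 11.5 instead give the later of 1 month and resolution of related events. Neither provides systematic follow-up from day 31 to 6 months.

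**The case against.** The strongest reply is that the plan does indicate an order. The first paragraph of Section 10.6 uses the word primary and the second says only that an analysis will be done; Section 7.5 and the Synopsis independently keep failed attempts out of the primary analysis group. Specific before general, the implanted set is primary and ITT supportive. This stands: a reader might infer that the plan gives no hierarchy for safety at all, and the text does not support that. What is missing is the sentence that says so.

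A reader might also infer that a death in a failed attempt would go unreported. That is not supported either. The patient is enrolled, so the event belongs in the ITT safety proportion; failed attempts must be listed in the final report; and Section 9.1 has the events committee review neurologic, device-related and procedure-related serious events.

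Nor can one say that the primary rate must be too low, as step 5 shows. It is also too strong to call implanted status wholly undefined: Section 7.5 turns on whether the device was placed within the aneurysm.

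Finally, the study is descriptive (Sections 10 and 10.1) with no safety threshold, so no formal decision turns on the difference. An attempted set has its own weakness: late follow-up is incomplete, and failed-attempt patients received alternative treatment, so later events may reflect that treatment. Both are fair. Keeping the implanted set primary and calling ITT supportive would cure the ambiguity, but the primary rate would remain conditional on successful placement.

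**Conclusion.** The concern holds in a limited form and should be fixed. The rule labelled primary for safety selects on procedural success, and the plan does not say what the ITT analysis of the same endpoint is for. The harm is a headline rate that answers a narrower question than it appears to, not lost data.

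One event in a failed attempt would move the rate by about 1.7 points in the main illustration (2.0% to 3.6%), well inside the sampling uncertainty. With no such event the shift is 0.2 points or less in the other direction. These sizes rest entirely on assumed counts of failed attempts and events. The textual finding does not.

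The same wording might suggest a parallel problem with the occlusion rate, or with what the target of 51 counts. Those are separate questions. For occlusion, how failed attempts would be handled is only an inference from the text, so no conclusion on it is drawn here.

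**What to change.** - In Sections 10.2 and 10.6, define the primary safety set as all patients in whom Neqstent delivery was attempted. Keep the implanted-only set as secondary. Leave consented patients with no attempt out of both, and state what role, if any, ITT has for safety.
- Align the enrolment scenarios in the Synopsis and Section 7.5 with these definitions.
- Report the 30-day component for all attempted patients, and state that the day 31 to 6 month component is incomplete for failed attempts.
- Reconcile the two statements on follow-up of failed attempts (Section 7.5 and the Synopsis scenarios against the Synopsis duration text and Section 11.5).

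The sample size need not change. The cost is slightly more analysis work, a possibly less favourable safety rate, and incomplete late follow-up in a few patients who received alternative treatment. The sets should be fixed before results are known, so that the choice cannot follow the data.

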#### **Endpoint Analysis:**

The primary performance endpoint will be calculated as the proportion of subjects with complete occlusion demonstrated with a Grade 1 on the Raymond Roy Scale at 6 months follow-up. In the event of a Grade 2 or more using the Raymond Roy Scale, a second assessment will be made at 12- month follow-up to re-assess for complete occlusion and will be reported as a secondary efficacy.

For AE reporting, both subject counts and event counts will be presented in tabular summaries of results.

A summary of subjects with protocol deviations will be reported but those subjects will be included in all analyses although endpoints may be summarized without the subjects (per-protocol analysis group) to provide additional information but not for the primary analysis.

For continuous variables, statistics will include means, standard deviations, medians and ranges. Categorical variables will be summarized in frequency distributions. Missing data will not be imputed. The number of data values available for each analysis will be reported so that the impact of missing data can be seen.

Statistical analyses will be conducted in SAS version 9.4 or above (SAS Institute, Cary, N.C.).

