## 7.9 Follow-Up

Following discharge, the subject will have a follow-up visit at 1 month, 6 months, 12 months and 24 months after the implant procedure. At each study visit, the subject shall be assessed for any new adverse events (AEs). A standard neurologic examination should be performed to evaluate for any new adverse events. A modified Rankin Scale (mRS) will be recorded at each follow-up visit. It is expected that most target IAs will be asymptomatic and the likelihood of post-placement neurologic changes is very low. The NIH Stroke Scale assessment should be obtained within 24 hour after a stroke in the event a subject is diagnosed with a stroke. Cerebral angiography will be repeated at 6 months and 12 months (if the Raymond Roy scale is Grade 2 or higher at 6 months). The cerebral angiography will include a 3D angiogram. The investigator should ensure that follow-up angiography is done with identical views to maximize the ability to compare baseline and post-treatment views. All angiographic images should be submitted to the independent core laboratory following the image transfer protocol. The target IA status shall be evaluated by an independent core laboratory.

The study's schedule of assessments and post-treatment visit windows are shown in

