# Baseline image screening can be completed within 3 months prior to enrollment. Imaging will always be performed on the day of the procedure which will be used for core laboratory baseline for comparison at 6 months.

\* The NIH Stroke Scale score should be obtained within 24 hours after stroke in the event a subject is diagnosed with a stroke.

\*\* mRS will be obtained at all scheduled visits.

\*\*\* Cerebral angiogram is required at 6 months only; in the event of a Grade 2 or more using the Raymond Roy Scale at 6 months, a second cerebral angiogram assessment will be made at 12-month follow-up to re-assess for complete occlusion and will be reported as secondary efficacy.

\*\*\*\* CTA is required at 6 months only; in the event of a Grade 2 or more using the Raymond Roy Scale at 6 months, a second cerebral angiogram assessment will be made at 12-month follow-up to re-assess for complete occlusion and will be reported as secondary efficacy.

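### Sections 10.2 and 10.6 define the per-protocol set differently, and the 10.6 wording, read literally, can raise the supportive occlusion rate by removing 6-month failures for a 12-month lapse that successes cannot have

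*Combined protocol and SAP*

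**What the plan says.** Section 10.2 (Patient Population) sets an entry condition: "The PP population will include subjects who complete 6 months of follow-up, die prior to their 6-month clinic visit, or are study failure", where study failure means withdrawal to obtain alternate treatment. It then sets an exclusion: "The PP will exclude patients with any major protocol violation that affects proper study inclusion or significant outcomes". It also makes the analysis a commitment: "Endpoints will be evaluated in the PP and ITT populations".

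Section 10.6 (Endpoint Analysis) starts from the opposite default: "A summary of subjects with protocol deviations will be reported but those subjects will be included in all analyses". It then allows an exception: "endpoints may be summarized without the subjects (per-protocol analysis group) to provide additional information but not for the primary analysis". This text has no severity qualifier, no time limit and no follow-up condition, and it does not refer back to 10.2.

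On imaging, the Table 8 footnote in section 7.9 says "Cerebral angiogram is required at 6 months only", and for the 12-month visit it adds: "in the event of a Grade 2 or more using the Raymond Roy Scale at 6 months, a second cerebral angiogram assessment will be made". Section 10.4.1 defines performance success as Raymond Roy Grade 1 at 6 months. Section 12.1.14 requires every deviation to be documented but does not separate major from minor.

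**The concern.** One label covers two membership rules, and a programmer could defend either. The choice affects the result because of the imaging schedule. The 12-month angiogram is required only of subjects already counted as failures for the 6-month endpoint. If any deviation removes a subject, a lapse that occurs after the endpoint is known, and that is open only to failures, can remove a valid failure from the denominator.

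At stake is how the supportive PP occlusion rate is read. The trial has a single arm, so there is no control group in which the same exclusion could cancel. Section 10 leaves the assessment of performance to clinical judgement of the data. With two rules in the plan, the choice between them could also be made after the results are known.

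**Working it through.** **The two rules side by side.** Failure here means Grade 2 or more at 6 months.

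| | 10.2 | 10.6, read literally |
|---|---|---|
| Removed | Major violations affecting inclusion or significant outcomes | Subjects with protocol deviations |
| Follow-up condition | 6 months completed, death before that visit, or study failure | None stated |
| Time limit on the deviation | None stated | None stated |
| Status | *Will* be evaluated | *May* be summarized; not primary |

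Two example records show the difference:

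- A subject has the 1-month visit at day 40 (window 1 month ± 1 week) and Grade 1 at 6 months. Unless the late visit is called major, the subject is in under 10.2 and out under 10.6. This removes a success.
- A subject has Grade 2 at 6 months and misses the 12-month angiogram. Unless the miss is called major, the subject is in under 10.2 and out under 10.6. This removes a failure whose 6-month outcome is complete. A Grade 1 subject cannot have this deviation.

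**The plan's own figures.** Section 10.6 gives 70% and 55% success, a 10% margin, one-sided 5% significance, 80% power, 46 evaluable and 51 enrolled.

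- (1.645 + 0.842)² × (0.55 × 0.45 + 0.70 × 0.30) / (0.15 + 0.10)² = 6.185 × 0.4575 / 0.0625 = 45.3, which rounds up to 46. This is the per-arm formula of a two-arm non-inferiority comparison, which is a separate matter.
- 46 × 1.10 = 50.6, which rounds up to 51 (46 / 0.90 = 51.1 would round up to 52).

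The documents give no PP size, PP rate or deviation rate, so there is no PP figure to reproduce.

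**Size of the effect.** Let p be the 6-month Grade 1 rate and m the share of failures removed only because of the 12-month angiogram. Deviations equally common in successes and failures cancel, so

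PP rate = p / [p + (1 − p)(1 − m)].

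The values of m are assumptions, shown as a range.

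| m | p = 70% | p = 55% |
|---|---|---|
| 0% | 70.0% | 55.0% |
| 10% | 0.70 / 0.970 = 72.2% (+2.2 points) | 0.55 / 0.955 = 57.6% (+2.6) |
| 20% | 0.70 / 0.940 = 74.5% (+4.5) | 0.55 / 0.910 = 60.4% (+5.4) |
| 30% | 0.70 / 0.910 = 76.9% (+6.9) | 0.55 / 0.865 = 63.6% (+8.6) |

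At p = 70% there are 46 × 0.30 = 13.8 failures, so these shares are 1.4, 2.8 and 4.1 subjects.

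In whole subjects, 32/46 = 69.6%. Removing one such failure gives 32/45 = 71.1%, two give 32/44 = 72.7%, and four give 32/42 = 76.2%. To cancel one removal, 32/14 = 2.3 successes would have to be dropped for other deviations.

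**The case against.** The strongest reply is that 10.6 does not set out to define a population. Its operative rule keeps subjects with deviations in all analyses. The parenthesis can be read as a loose pointer to the set already defined in 10.2, and the text nowhere says that every subject with any deviation is dropped. This is a fair reading of what was probably meant. It does not settle the matter, because the words attach the label to the set left after removing deviators and there is no cross-reference.

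A reader might also infer that an inflated PP rate will be reported beside the primary result. The documents do not support that. The commitment in 10.2 attaches to 10.2's own population, while the 10.6 summary is optional and explicitly not primary. The inflation further requires that 12-month angiograms are missed or late and that the lapse is logged as a deviation. Section 7.10 accepts loss to follow-up and withdrawal of consent as valid reasons for leaving, so some missed angiograms may be recorded that way instead. Grade 1 subjects still have 12- and 24-month visits and can deviate there; only the angiogram is specific to failures.

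The missing follow-up condition in 10.6 should not be overread either. A subject lost at month 3 has no 6-month angiogram, and missing data are not imputed, so the occlusion rate is the same with or without that subject. At most the safety denominator changes.

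Finally, 10.2 alone is not a full safeguard. It does not say what counts as major or as a significant outcome, and a missed 12-month angiogram, which feeds a secondary efficacy endpoint, could be classed as major. This stands, and the fix has to deal with it.

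**Conclusion.** The inconsistency is real: 10.2 and 10.6 differ on severity, on the follow-up condition and on whether the analysis is optional. Read literally, the 10.6 rule can raise the supportive PP occlusion rate. At the planning rate of 70% the rise is 2.2 to 6.9 points if 10% to 30% of failures are removed only for the 12-month angiogram. Those shares are assumptions. The rise is zero if no such angiogram is missed or late, and more frequent deviations of other kinds among successes can offset it.

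A reader might go further and conclude that the trial's main result is biased. It is not. Under section 10.6 the primary analyses use the intent-to-treat and safety populations, and neither they nor the sample size of 46 and 51 depend on the PP rule. Nor does the plan present agreement between PP and intent-to-treat results as a test of robustness; the point is only that such agreement could not bear that weight while the PP rule is unsettled. This is a supportive-analysis issue that should be corrected because the change is small.

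**What to change.** - In 10.6 (Endpoint Analysis), replace the wording that equates the per-protocol group with the subjects left after removing deviators by a reference to the Per Protocol population defined in 10.2.
- In 10.2, state that for the 6-month endpoints only major violations occurring up to and including the 6-month assessment exclude a subject. Later deviations, including a missed or late 12-month angiogram, do not.
- In 10.2, define which violations are major and state that the list is fixed before core-laboratory reads are known.

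The cost is a few sentences of analysis wording, with no new data, visits or patients. The downside is that the PP set keeps subjects with minor or late deviations, so its occlusion rate may look slightly less favourable.

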## 10 Statistical Analysis

This study intends to examine the safety and performance of the Neqstent used for the treatment for embolization of intracranial aneurysms. The study is not powered to detect statistical significance. As such, clinical judgement is required to assess device safety and performance from the data collected during this study. Clinical judgement will be provided throughout the study by the DSMB.

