## 10.6 Sample Size Rationale and Statistical Considerations

This is a single arm study designed to provide adequate data for the purpose of a pre-market study. It is expected the 51 patients with evaluable data at 6 month and 12 month follow-up (where necessary) will show adequate evidence of safety and performance of Neqstent device.

For the purpose of sample size calculation, the primary outcome measurement is assumed to be the composite of the listed primary endpoint components.

Extensive literature search was conducted to gather information on the non-inferiority margin. Due to limited results found in literature, the non-inferiority margin for this study,  $\delta = 10\%$ , was chosen to align with the study design.

The sample size estimation was based on the following assumption:

- Success rate of the investigational is expected to be 70%
- Success rate of standard treatment is estimated to be 55%
- Power is set at 80% and one-sided significance level is set at 5%
- Expected rate of attrition is 10%

Based on the assumptions, a total of 46 subjects are required to show that the expected success rate of 70% is different than the true rate of 55% with a delta of 10%. Adding in additional subjects for anticipated loss to follow-up, 51 subjects are needed to be enrolled for a total of 46 subjects with 6 month data.

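### Section 10.6 sizes the trial for a one-sided 5% non-inferiority comparison that its analysis text never makes, while sections 10 and 10.1 call the study descriptive and unpowered

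*Combined protocol and SAP*

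**What the plan says.** All references are to the combined protocol and SAP.

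- **Sample size (section 10.6).** The design is introduced thus: "This is a single arm study designed to provide adequate data for the purpose of a pre-market study". On the margin, "Extensive literature search was conducted to gather information on the non-inferiority margin"; little was found, and 10% was chosen. The assumptions are "Success rate of the investigational is expected to be 70" per cent, "Success rate of standard treatment is estimated to be 55" per cent, and "Power is set at 80% and one-sided significance level is set at 5" per cent. The result is 46 subjects with 6-month data and 51 enrolled. The outcome used for sizing is said to be a composite of the primary endpoint components. The subjects with evaluable data, it says, "will show adequate evidence of safety and performance of Neqstent device".
- **Analysis (section 10.6, Analysis Population and Endpoint Analysis).** The safety endpoint and the occlusion endpoint are each defined as a proportion of subjects. For the rest, "Categorical variables will be summarized in frequency distributions". Missing data are not imputed, and the number of values behind each analysis is reported.
- **Status (sections 10 and 10.1).** Section 10 says that the study has no power for statistical significance, so that "clinical judgement is required to assess device safety and performance from the data collected during this study". Section 10.1 calls it a descriptive study.
- **Elsewhere.** Success in the synopsis and in section 10.4.1 is a grade for the individual subject (Raymond Roy Grade 1), not a rule for the study. Section 12.2.19 promises statistical analysis in the report where it is suitable, without naming a method.

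**The concern.** The enrolment figure comes from a formal comparison with an error rate, a power and a margin. The analysis text contains no hypothesis, test, confidence limit, reference value or study-level criterion. If the plan is followed as written, the comparison that justified 51 subjects is not carried out, and whether the evidence is adequate is left to judgement after the percentages are known.

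The final report goes to ethics committees, regulatory authorities and the notified body (section 12.1.15). With about 46 subjects a percentage alone says little about what has been excluded. A result near the expected rate is compatible with a wide range, and no safety events at all would still leave a rate of 5% unexcluded. A bar chosen after the data are seen would carry little weight.

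**Working it through.** **1. Reproducing the plan's 46.** Inputs from section 10.6: p1 = 0.70, p0 = 0.55, margin 0.10, one-sided 5% (z = 1.645), power 80% (z = 0.842). The two-sample non-inferiority formula with unpooled variance is

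n = (1.645 + 0.842)² × [0.70 × 0.30 + 0.55 × 0.45] / (0.70 − 0.55 + 0.10)²

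= 6.18 × 0.4575 / 0.0625 = 45.3, rounded up to **46**.

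The stated figure therefore does come from a one-sided 5% non-inferiority calculation. At one-sided 2.5% the same formula gives 58. For attrition, 46 × 1.1 = 50.6 gives 51; 46 / 0.9 = 51.1 would give 52.

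**2. What that 46 is.** It is the per-arm size of a two-arm comparison, and this trial has one arm. A one-sample calculation against a fixed 45% (55% − 10%) gives

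n = [(1.645 × √(0.45 × 0.55) + 0.842 × √(0.70 × 0.30)) / 0.25]² = 23.2, so 24.

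Against a fixed 55% the same formula gives 64.4, so 65. Neither is 46. The arithmetic shows a non-inferiority intent but does not identify the single-arm bound.

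**3. Precision at the planned size.** Clopper-Pearson limits for x of n: the lower limit is the α quantile of Beta(x, n − x + 1), and the upper limit is the 1 − α quantile of Beta(x + 1, n − x). One-sided 95% limits use α = 0.05; two-sided 95% intervals use α = 0.025 on each side.

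| Result | Rate | One-sided 95% limit | Two-sided 95% interval |
|---|---|---|---|
| Occlusion 32/46 | 69.6% | lower 56.6% | 54.2% to 82.3% |
| Occlusion 36/51 | 70.6% | lower 58.4% | 56.2% to 82.5% |
| Safety 0/51 | 0% | upper 5.7% | – |

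The 0/51 limit is 1 − 0.05^(1/51) = 5.7%. The interval is 82.3 − 54.2 = 28.1 points wide at 32/46 and 82.5 − 56.2 = 26.3 points wide at 36/51. At 32/46 the one-sided limit lies above 55% and the two-sided limit below it, so the sidedness also has to be stated.

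**4. What an unstated bound leaves open (46 evaluable, exact binomial).**

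| Assumed fixed bound | Smallest passing count | Type I error | Power at a true 70% |
|---|---|---|---|
| 45% | 27/46 (58.7%; lower limit 45.5%) | 4.3% | 96% |
| 55% | 32/46 (69.6%; lower limit 56.6%) | 3.2% | 60% |

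Any count from 27 to 31 of 46 passes under the first bound and fails under the second. Section 10.6 mentions a margin, which points to 45%, but it also speaks of a difference from 55%.

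**The case against.** The strongest reply is that the plan states its position openly. Sections 10 and 10.1 say that the study is unpowered and descriptive, and the objective is only to document safety and performance. Proportions without a test are consistent with that. Denominators will be reported, so a reader could work out any interval, and clinical judgement is to draw on the data collected, not on a point estimate alone. No data are lost and no subject is affected.

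Much of this stands. It means that the fault is a contradiction between sections 10 and 10.1 on one side and section 10.6 on the other, and that adding a test is not the only remedy. It does not remove the fault. Section 10.6 still states 80% power and still promises adequate evidence, and a descriptive study also needs a stated measure of precision.

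A reader might go further and infer that 45% is the plan's own bar, so that 26/46 (56.5%, one-sided 95% lower limit 43.4%) would look better than standard treatment yet fail. The documents do not support that. No section states 45%, and step 2 shows that the 46 was not computed against it. The sizing is on a composite, and nothing says that 55% is the standard-treatment rate for Grade 1 occlusion alone. No reference rate for safety is given at all.

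**Conclusion.** The point holds as an internal contradiction together with an omission. The sample size rests on a one-sided 5%, 80%-power non-inferiority calculation, which reproduces at 45.3, rounded up to 46. The analysis reports bare proportions, and two other sections deny that the study is powered. The endpoint used for sizing (a composite) is not the one analysed either, since safety and occlusion are reported separately.

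The practical size is the imprecision left unreported, about 28 points of interval width at the expected occlusion result and a 5.7% upper limit with no safety events, and the 27-to-31 band of results that the plan cannot classify. The limits assume 46 evaluable subjects for occlusion and 51 for safety. The pass marks also assume that 55% applies to the analysed endpoint, that the reference is a fixed value and, for the 27/46 mark, that the margin is simply subtracted.

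It would be tempting to require a second test against 55% after non-inferiority. The plan makes no superiority claim, and that step would have only about 60% power at a true 70%, so it should not be prescribed.

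**What to change.** **In section 10.6, under either intent:** report each primary proportion with its exact (Clopper-Pearson) two-sided 95% interval and the one-sided 95% limit, lower for occlusion and upper for safety.

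**Then, before outcomes are seen, choose one:**

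- **(a) Keep the non-inferiority aim.** Name the endpoint it applies to (occlusion or the composite), state and justify the fixed bound, and remove the unpowered and descriptive wording from sections 10 and 10.1. If the bound is set at 45%, write the rule as at least 27/46, with the type I error and power shown in step 4, and recompute it for the number actually evaluable.
- **(b) Keep the study descriptive.** Withdraw the power and non-inferiority rationale and the claim of adequate evidence, and justify 51 by the interval widths in step 3.

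The cost is a few sentences and a few lines of SAS, with no extra subjects or data. Option (a) also needs a justification for the reference rate and margin that the documents do not now give. The downside for the sponsor is that results will read less favourably with their limits attached.
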